## 8.2.2 Replacement Policy

Study subjects who have been assigned to a group and drop out prior to the first group session can be replaced by a new subject who will be assigned to the same group. Subjects who drop out after the first group therapy session will not be replaced.

## 8.2.3 Accrual estimates

The annual number of eligible patients is high given the size of the population of HIV-seropositive gay-identified men in the San Francisco Bay Area. In 2014, San Francisco reported 15,979 people living with HIV, 14,221 of whom were men who have sex with men, and 9,202 of whom are 50 and older [8]. If accrual falls short of expectations, advertising and recruitment efforts will be expanded.

## 8.3 Interim Analyses and Stopping Rules

After the occurrence of one Adverse Event judged to be Severe and potentially related to the drug/intervention, enrollment will be stopped until a Safety Review has been completed and the appropriate protocol amendments implemented.

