#### *Rationale for Dosing Regimen*

Griffiths et al [138] have characterized the dose-response relationship of oral psilocybin in healthy volunteers. They found that when considering the odds of attaining a complete mystical experience versus having a temporary anxiety reaction during the drug experience (lasting on the order of minutes), the optimal dose likely falls between 0.29mg/kg and 0.43mg/kg [138]. This dose range has been successfully used in studies of psilocybin-assisted psychotherapy for existential distress in cancer patients [19, 20], severe alcohol use disorder [107] and tobacco use disorder [108]. The current study will employ a dose of 0.3mg/kg po in the first group, and if this is well tolerated will then escalate to 0.36mg/kg po in subsequent groups.

The dosing of the psychotherapy—8 weekly sessions—was chosen on the basis of comparison with similar group psychotherapies for existential distress in palliative care patients. The group psychotherapy with the best evidence-base for treating existential distress in palliative care patients, Meaning-Centered Group Psychotherapy, also employs 8 sessions [139]. The group psychotherapy with the best evidence-based for treating complicated grief has 16 weekly sessions [140]. Our protocol uses a modified course of Brief Supportive-Expressive Group Therapy, which was designed and tested as a 12-week course of treatment [76]. Empirical data suggest that group therapies lasting at least 12 sessions are shown to have greater correlations between group cohesion and clinical outcomes [129]. We hypothesize that psilocybin will catalyze group cohesion in a shorter period of time, thus making 12-16 weeks of group therapy unnecessary for detecting comparable results with regards to cohesion and clinical outcomes.

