### 3.4 Duration of Therapy

In the absence of treatment delays due to adverse events, treatment may continue for 8 weeks or until:

- Inter-current illness that prevents further administration of treatment
- Unacceptable adverse event(s)

---

 Individuals taking antidepressants, anxiolytics and stimulants will be presented with the option of tapering off, and remaining off, of their medication for the duration of the study, if their prescribing physician agrees with this course of treatment.

- Patients decides to withdraw from the study
- Significant patient non-compliance with protocol
- General or specific changes in the patients' condition render the patient unacceptable for further treatment in the judgment of the investigator.

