## 6.4.2 In-person Screening and Enrollment

Screening procedures and assessments to be completed on day of Enrollment (prior laboratory results from UCSF clinics may be considered instead of performing labs at enrollment if the results are less than 6 months old):

- Demographics questionnaire (Age, ethnicity/race, civil status, years of education, income)
- Vital signs; Physical examination; Complete medical and psychiatric history, including current medication list; Performance status (PPSV2); Mental Status Exam; Cognitive Status (Montreal Cognitive Assessment)
- Complete blood count (WBC, Hgb, Hct, Plt)
- Comprehensive metabolic panel (Na, K, Cl, CO2, BUN, Cr, Gluc, Tbili, Ast, Alt, AlkPhos, TProt, Alb)
- TSH, FT4
- Urinalysis
- Urine toxicology (must be completed on day of Enrollment)
- HIV viral load, CD4 count, CD8 count
- RPR or Treponemal Antibody
- Electrocardiogram (ECG)
- Selected screening portions of Structured Clinical Interview for DSM-5 Clinical Trials Version (SCID-5); sections on current Depressive disorders; lifetime Psychotic disorders, Bipolar disorders and Hallucinogen-related disorders), Structured Clinical Interview for DSM-5 Personality Disorders, self-report version (SCID-5-PD; section on Cluster B disorders)
- Columbia Suicide Severity Rating Scale (C-SSRS): Baseline/Screening (last 12 months)
- ART Medication Adherence Scale (AMAS), Centers for Epidemiologic Studies Depression Scale—Revised (CESD-R), Demoralization Scale—II (DS-II), Inventory of Complicated Grief (ICG), McGill Quality of Life Questionnaire-Revised-Short (MQoL-RS), PTSD Checklist-5 (PCL-5), Schedule of Attitudes towards Hastened Death (SAHD), State-Trait Anxiety Inventory (STAI).

Upon completing a successful in-person screening, subjects will also meet individually with one of the study therapists for 30 minutes to develop rapport and to discuss details about the subject's personal life, such as past and current relationships, family dynamics, and concerns about their disease. Finally, the subject will be placed on the waitlist until 6 subjects are available to start a group.

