### 6.4.4.2 Individual Drug Sessions (Weeks 4-5)

Patients will undergo individual drug sessions in which they are administered psilocybin 0.30mg/kg (or 0.36mg/kg) po, with a maximum dose not to exceed that calculated for a BMI of 35 at their height. The drug will be administered following the safety guidelines outlined by Johnson et al [24].

The day prior to the session, patients will be screened over the phone for contraindicated medications and reminded about procedures for the medication visit. **Specifically, participants will be reminded that they cannot drive an automobile for the rest of the day after their medication visit, and they will be advised that if they will take the BART, they should not drive their car to the BART station.**

On the day of the medication visit, patients will arrive at the Langley Porter Psychiatric Institute by 08:00 and be oriented to the drug session room, which will contain a couch for the patient to lie on and aesthetically pleasing décor. Before the medication session starts, participants will complete a urine drug screen and the CrEQ. Participants will then hand over their shoes, keys, wallet and phones to the study therapists for safe keeping; these will all be returned to the patient upon completion of the treatment session.

The entire session will be audio and video recorded for subsequent behavioral analysis and rating of therapist adherence to the therapy protocol. The patient will ingest the psilocybin capsules with 4 ounces of water and then be instructed to lie down on the couch wearing

eyeshades and listening to a preselected music soundtrack via headphones. The subject will be instructed to focus their attention internally and to attempt to interact minimally with the two therapists who will be present in the room throughout the drug session, but will be as non-directive as possible in their interactions with the patient. In the event of a psychologically challenging experience such as significant anxiety or confusion, the therapists will provide verbal reassurance. Patients will have been instructed in the preparatory therapy session to notify the study therapists if during the treatment they feel anxiety or fear.

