## 6.5 Discontinuation of Therapy

The Investigator will withdraw a patient whenever continued participation is no longer in the patient's best interest. Reasons for withdrawing a patient include, but are not limited to, disease progression, the occurrence of an adverse event or a concurrent illness, a patient's request to end participation, a patient's non-compliance or simply significant uncertainty on the part of the Investigator that continued participation is prudent. There may also be administrative reasons to terminate participation, such as concern about a patient's compliance with the prescribed treatment regimen.

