## 7.6 Adverse Events Monitoring

All adverse events, whether or not unexpected, and whether or not considered to be associated with the use of the study drug, will be entered into UCSF REDCap, as noted above.

The Investigator will assess all adverse events and determine reportability requirements to the Data and Safety Monitor (DSM) and UCSF's Institutional Review Board, the Committee on Human Research (CHR); and, when the study is conducted under an Investigational New Drug Application (IND), to the Food and Drug Administration (FDA) if it meets the FDA reporting criteria.

In addition, all adverse events and suspected adverse reactions considered "serious," entered into UCSF REDCap will be reviewed and monitored by the Data and Safety Monitor on an

ongoing basis, discussed at DSM meetings which take place after each therapy group completes the 8-week intervention.

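### The 8.3 stopping rule halts enrollment but not dosing, so it does not hold the remaining psilocybin sessions of subjects already enrolled

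*Combined protocol and SAP*

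**What the plan says.** Section 8.3 of the combined protocol and SAP has one trigger and one action: "After the occurrence of one Adverse Event judged to be Severe and potentially related to the drug/intervention, enrollment will be stopped". The stop lasts until a Safety Review is complete and the resulting amendments are in place. Dosing is not mentioned.

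The order of enrollment and dosing is set elsewhere:

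- 6.4.2: after a successful in-person screen, "the subject will be placed on the waitlist until 6 subjects are available to start a group".
- 8.2.2: "Subjects who drop out after the first group therapy session will not be replaced".
- 6.4.4.1 and 6.4.4.2: group sessions 1-4 run in Weeks 2-3, two per week. The single psilocybin dose is given in an individual session in Weeks 4-5.
- 1.3, dosing rationale: the first group receives 0.3 mg/kg, and "if this is well tolerated will then escalate to 0.36mg/kg po in subsequent groups".
- 7.6: serious events are reviewed by the Data and Safety Monitor on an ongoing basis and "discussed at DSM meetings which take place after each therapy group completes the 8-week intervention".

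**The concern.** The risk that 8.3 responds to arises from taking psilocybin, and safety is part of the primary objective. The sponsor has already decided that one Severe, potentially related event is enough to require a review before more people are brought in. The action chosen does not reach the people closest to the next exposure, who are the undosed members of the same group. They are already enrolled, as are subjects on the waitlist.

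The matter is sharper at escalation. The second group may be the first to receive 0.36 mg/kg, and the condition that the lower dose be well tolerated operates between groups. If the first subject dosed at 0.36 mg/kg has a triggering event, nothing in 8.3 delays the same dose for the rest of that group.

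**Working it through.** The plan gives no operating characteristic for this rule, so there is no figure to reproduce. The check is of the timeline first, then of the counts.

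**Reading of the trigger (assumption).** Severe is taken as Grade 3 or higher, and potentially related as Possible, Probable or Definite, on the scales in 7.4.

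**Timeline of one group**

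| Step | When | Source |
|---|---|---|
| Enrolled, then waitlisted until six are available | before Week 1 | 6.4.2 |
| Baseline | Week 1 | 6.4.3 |
| First group session; no replacement afterwards | Week 2 | 6.4.4.1, 8.2.2 |
| Psilocybin, individual sessions | Weeks 4-5 | 6.4.4.2 |
| Group sessions 5-10 | Weeks 6-8 | 6.4.4.3 |
| Scheduled monitor meeting | after the 8 weeks | 7.6 |

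The nominal lag from closing the group to its first dose is 4 - 2 = 2 weeks. The scheduled monitor meeting falls after all of the group's doses.

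**Groupmates not reached.** Assume six members dosed one at a time; the protocol does not state the spacing. If the first triggering event is in the k-th member dosed, 6 - k doses remain: 5, 4, 3, 2, 1 or 0, with mean 15/6 = 2.5 if each position is equally likely. If two are dosed per day, 4, 2 or 0 remain. These are upper bounds, because members who leave after the first session are not replaced.

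**Last group.** Once it is enrolled, no enrollment remains in the trial. With three groups of six, this covers up to 6/18 = 33% of doses; at the maximum of six groups, up to 6/36 = 17%.

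**Illustration only.** The documents give no usable rate of such events for this population. With an assumed independent risk p per subject:

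- chance of at least one trigger in 18 = 1 - (1 - p)^18
- chance that a groupmate is still undosed, given a trigger in a group of six = 1 - p(1 - p)^5 / [1 - (1 - p)^6]
- chance of a second such event in that group, given a first = P(at least 2 of 6) / P(at least 1 of 6)

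| p | Trigger in 18 | Groupmate still undosed | Mean number undosed | Second event in group |
|---|---|---|---|---|
| 2% | 30.5% | 84.2% | 2.56 | 5.0% |
| 5% | 60.3% | 85.4% | 2.65 | 12.4% |
| 10% | 85.0% | 87.4% | 2.81 | 24.4% |

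For p = 5%: P(at least 1 of 6) = 1 - 0.95^6 = 0.2649; 1 - 0.0387/0.2649 = 0.854; 0.0328/0.2649 = 0.124.

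The chance of a trigger depends heavily on p. The chance that someone is still undosed hardly does.

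**Other provisions that might supply a hold**

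- 3.4 and 6.5: treatment ends or a patient is withdrawn, one patient at a time, on the investigator's judgment.
- 5.1: concerns the affected patient only.
- 7.6: ongoing monitor review of serious events, with no hold attached.
- 7.7: notice to the monitor within one business day, for related deaths only.
- 9.4: an amendment may precede IRB approval to remove an immediate hazard. This is permitted, not required.

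None requires the other members' sessions to wait.

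**The case against.** The strongest reply is that the protocol gives the investigator ample means to pause. Section 6.5 is framed as an obligation: "The Investigator will withdraw a patient whenever continued participation is no longer in the patient's best interest". Its reasons include mere uncertainty about whether continuing is prudent, and a severe drug reaction in a groupmate would meet that easily. Section 9.4 offers a trial-level route that can act at once. Section 3.4 already foresees delay: "In the absence of treatment delays due to adverse events, treatment may continue for 8 weeks or until". A study physician is on site for every dose. In a single-site, open-label pilot with one dose per subject, an automatic hold may add little to sound judgment. This stands in part: a responsible investigator would probably pause. But a stopping rule is written so that the pause does not depend on judgment on the day.

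A second reply is that the assumed risks lean high. Section 4.1.1 reports no significant adverse events at another centre in about 270 subjects and 560 sessions. Zero events in 270 gives a 95% upper bound of 1 - 0.05^(1/270) = 1.1% per subject, or about an 18% chance of a trigger in 18. Counted by session, the bound is 0.5% and the chance about 9%. Significant is not the same as Grade 3, and the population differs, so this is only indicative. It does confirm that the trigger probabilities should carry no weight.

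Three stronger readings are tempting and not supported:

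- A reader might infer that nothing in the trial can hold dosing. The discretionary routes above exist, and the Data and Safety Monitoring Plan that 9.7 places in an appendix was not available and could contain a hold.
- A reader might take the minimum of eight subjects in two groups of four and conclude that half of all doses fall after enrollment ends. Eight is a minimum for completers (3.2, 8.2.1), not a number of doses.
- A reader might call the rule empty. It still stops recruitment to later groups until the last group is enrolled.

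**Conclusion.** The point holds within the text reviewed. Section 8.3, followed exactly, does not delay psilocybin for up to five undosed members of the affected group or for subjects enrolled and waiting. After the last group is enrolled, it has no effect. The other provisions allow a pause without requiring one.

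The conclusion rests on the wording of 8.3 and the week-by-week schedule, not on any event rate. It assumes that the dose sessions in a group are not all given at the same time, and that the monitoring plan does not already contain a hold. If it does, 8.3 should refer to it. This is a gap in the reach of a safety rule that is worth closing, not evidence that subjects would in practice be dosed after a severe reaction.

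**What to change.** Extend the action in 8.3, for example:

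> After one adverse event of Grade 3 or higher rated Possible, Probable or Definite, enrollment, the start of any new group and all psilocybin sessions not yet given are held until the Safety Review is complete and any appropriate amendments are implemented. Safety follow-up and supportive or individual integration contact for dosed members continue. Group sessions 5-10 of the affected group wait until the review decides whether its remaining members will be dosed.

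The last sentence matters. If sessions 5-10 simply went ahead, they would be used up before some members were dosed, and the pre- and post-psilocybin comparison of group cohesion and process would be blurred. In 6.4, exempt these delays from the 7-day visit window.

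The change costs a few sentences and no new data. If the rule is triggered, there are real costs. The group's timetable lengthens, dosed members wait longer for their integration group sessions, and subjects who tapered off medication to take part stay off it longer. A prompt Safety Review limits all three.

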## 8.4 Analyses Plans

The study's biostatistician is [name]. Alongside the PI, [name] will be co-responsible for assuring that clinical data are correctly collected, stored and analyzed. He will work directly with the PI to assure that interpretations of these data are coherent and justified. [name] professional interests are rooted in the research, evaluation and implementation of evidence-based treatments for complex and severe mental disorders. As a Health Science Specialist at the Center for Innovation to Implementation (Ci2i), Veterans Affairs (VA) Palo Alto Health Care System, [name] investigates the clinical effects and implementation of evidence-based psychosocial treatments for psychotic, anxiety, and substance use disorders. His research utilizes a variety of assessment (e.g., structured clinical interviews, biological assays) and statistical (e.g., linear mixed models, exploratory structural equation modeling) techniques. As a Senior Evaluator at the Program Evaluation and Resource Center (PERC), VA Office of Mental Health Operations (OMHO), [name] supports OMHO's nationwide program evaluation and quality improvement efforts.

### 8.4.1 Analysis Population

All patients who enroll in the study will be included in analyses of safety and tolerability.

All patients who make any contact at all with the study (including those who are screened out over the phone) will be included in analyses of feasibility.

All patients who enroll in the trial will be included in analyses of efficacy. Repeated efficacy measures will be gathered and trended, regardless of missing data or protocol non-adherence.

All patients who participate in at least one group therapy session will be included in analyses of psychotherapeutic process.

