### 2.2 Endpoints

#### 2.2.1 Primary Endpoints

- Safety will be defined based on the rate of adverse reactions (defined by the NIH Division of AIDS Table of Grading of Severity of Adult and Pediatric Adverse Events V2.0) (see Section 5 below). The safety of acute drug effects will be assessed by monitoring vital signs for tachycardia (HR>100bpm), bradycardia (HR<60bpm), hypertension (SBP>140mmHg or DBP>90mmHg) and hypotension (SBP<100mmHg or DBP<60mmHg). Drug-induced mental status changes will be assessed using the Adverse Event Medication Session Rating Form during drug sessions, pre and post measures with the Montreal Cognitive Assessment, and the Persisting Effects Questionnaire—Spirituality at study follow up. Suicidality will be assessed with the Columbia Suicide Severity Rating Scale. Follow-up safety data will be gathered for 3 months.
- Feasibility will partially be assessed in terms of the rates of patient recruitment and retention. Feedback on acceptability will also be gathered from subjects and caregivers/important others using the Client Satisfaction Scale. Patients and caregivers will also be invited to provide feedback during a focus group and patients will be invited to participate in individual interviews after the intervention. A SEGT Topic Grid will be used to evaluate video recordings of group therapy sessions in order to assess therapist adherence to the PA-SEGT model.

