### 5.2 Monitoring and Toxicity Management

Of the hundreds of subjects administered psilocybin in clinical or research settings over the last two decades, none have required emergent psychiatric medications or emergency department care [24, 143, 154]. Each subject receiving psilocybin will be evaluable for safety. The safety parameters include physical findings and spontaneous reports of adverse events reported to the investigator by subjects and primary caregivers. Each subject will be assessed periodically for the development of any toxicity as outlined in [Section 6 Study Procedures and Observations](#). Toxicity will be assessed according to the NIH Division of AIDS Table of Grading of Severity of Adult and Pediatric Adverse Events V2.0 ([http://rsc.tech-res.com/Document/safetyandpharmacovigilance/DAIDS\\_AE\\_Grading\\_Table\\_v2\\_NOV2014.pdf](http://rsc.tech-res.com/Document/safetyandpharmacovigilance/DAIDS_AE_Grading_Table_v2_NOV2014.pdf))

. We will monitor specifically for hypertension, hypotension, tachycardia, nausea, emesis, headache, anxiety, dysphoria, mania, suicidality and psychosis during drug sessions using the Adverse Event Medication Session Rating Form (see Appendix). Acute physical adverse events (e.g., nausea or hypertension) will trigger increased frequency of monitoring. Acute psychological adverse events will be managed by supportive reassurance and, if needed, medications such as lorazepam or olanzapine. Further management of physical or psychiatric adverse events will depend upon the judgment of the on-call study physician and may include, if necessary, transportation to the UCSF Parnassus Emergency Department, which is located immediately adjacent to the Langley Porter Psychiatric Institute.

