### 7.3 Definitions of Adverse Events

#### 7.3.1 Adverse Event

An adverse event (also known as an adverse experience) is defined as any untoward medical occurrence associated with the use of a drug in humans, whether or not considered drug related. More specifically, an adverse event (can be any unfavorable and unintended sign (e.g., an abnormal laboratory finding), symptom, or disease temporally associated with the use of a drug, without any judgment about causality. An adverse event can arise from any use of the drug (e.g., off-label use, use in combination with another drug) and from any route of administration, formulation, or dose, including an overdose.

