#### 7.3.2 Adverse reaction

An adverse reaction is defined as any adverse event caused by the use of a drug. Adverse reactions are a subset of all suspected adverse reactions for which there is reason to conclude that the drug caused the event.

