## 7.4 Recording of an Adverse Event

All adverse events will be entered into UCSF REDCap, whether or not the event is believed to be associated with use of the study drug. Data about these events and their severity will be recorded using the NIH Division of AIDS Table of Grading of Severity of Adult and Pediatric Adverse Events V2.0.

The Investigator will assign attribution of the possible association of the event with use of the investigational drug, and this information will be entered into UCSF REDCap using the classification system listed below:

Relationship	Attribution	Description
Unrelated to investigational drug/intervention	Unrelated	The AE is clearly NOT related to the intervention
	Unlikely	The AE is doubtfully related to the intervention
Related to investigational drug/intervention	Possible	The AE may be related to the intervention
	Probable	The AE is likely related to the intervention
	Definite	The AE is clearly related to the intervention

Signs or symptoms reported as adverse events will be graded and recorded by the Investigator. When specific adverse events are not listed in the above NIH DAIDS Table of Grading of Severity, they will be graded by the Investigator as *none*, *mild*, *moderate* or *severe* according to the following grades and definitions:

- Grade 0 No AE (or within normal limits)
- Grade 1 Mild: Mild symptoms causing no or minimal interference with usual social & functional activities with intervention not indicated
- Grade 2 Moderate: Moderate symptoms causing greater than minimal interference with usual social & functional activities with intervention indicated
- Grade 3 Severe: Severe symptoms causing inability to perform usual social & functional activities with intervention or hospitalization indicated
- Grade 4 Potentially life-threatening: Potentially life-threatening symptoms causing inability to perform basic self-care functions with intervention indicated to prevent permanent impairment, persistent disability, or death
- Grade 5 Death related to AE

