## 8.5 Primary Analysis

Safety analyses will be performed for all patients who enroll in the study. The study will use the NIH Division of AIDS Table of Grading of Severity of Adult and Pediatric Adverse Events V2.0 to

classify adverse events. Descriptive statistics (percentages) will be reported for the incidence of any Adverse Events reported, including suicidality as measured by the C-SSRS. Median scores will also be calculated for total scores of the feasibility measures: CSS, CrEQ, and PEQ-S. The differences of mean pre- and post-treatment scores on the CORF will be calculated. Differences in individual pre- and post-treatment MoCA scores will be assessed for each individual. Therapist protocol adherence will be reported as a rate of discussion topic deviations from the protocol.

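### The planned safety summary (any adverse event, over all enrolled) does not give the adverse-reaction rate on which Section 2.2.1 bases primary safety

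*Combined protocol and SAP*

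**What the plan says.** **Endpoint.** Section 2.2.1 states: "Safety will be defined based on the rate of adverse reactions (defined by the NIH Division of AIDS Table of Grading of Severity", and the parenthesis goes on to name the grading table. Section 7.3.2 gives the term a causal meaning: "An adverse reaction is defined as any adverse event caused by the use of a drug". An adverse event under Section 7.3.1 is wider. It takes in any unfavourable sign, "symptom, or disease temporally associated with the use of a drug, without any judgment about causality".

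**Analysis.** Section 8.4.1 names the safety population: "All patients who enroll in the study will be included in analyses of safety and tolerability". Section 8.5 repeats it, "Safety analyses will be performed for all patients who enroll in the study", and specifies the summary: "Descriptive statistics (percentages) will be reported for the incidence of any Adverse Events reported, including suicidality as measured by the C-SSRS". Events are classified with the same DAIDS table. Section 8 names no set of dosed patients and plans no safety summary by onset, attribution or dose.

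**Data collected.** Section 7.4 has the investigator rate each event on five levels. The upper three (possible, probable, definite) are grouped as "Related to investigational drug/intervention". Within Section 8, relatedness is used only in the enrolment pause of Section 8.3.

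**Who is dosed, and when.** Section 5.2 says: "Each subject receiving psilocybin will be evaluable for safety". Under Section 6.4.2, enrolled patients wait until six are available. Four group sessions follow in Weeks 2-3 (6.4.4.1), and the drug session comes in Weeks 4-5 (6.4.4.2). Patients who drop out after the first group session are not replaced (8.2.2). Appendix A marks adverse-event screens before the drug session: five, as far as the table layout can be read.

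**The concern.** Safety is half of the primary objective, and the Abstract says the trial will supply the first safety data on this intervention in this population. A reader will want to know what share of those who took psilocybin had a reaction to it. The planned percentage answers a different question, in two ways.

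- **Numerator.** It counts every event, including those that began on the waitlist or during the preparatory sessions and those rated unrelated.
- **Denominator.** It includes patients who left before the drug session and so could not have had a drug reaction.

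These push in opposite directions, so one pooled percentage can sit above, below or on the drug-reaction rate. The reader cannot tell which from the planned table. The number dosed could be recovered from attendance, but without a split by onset and attribution the matching numerator could not.

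**Working it through.** The plan states no safety rate, so there is no figure to reproduce. The check compares the endpoint with the planned summary and then sizes the denominator effect.

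**Step 1. Endpoint against summary.**

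| Element | 2.2.1 read with 7.3.2 | 8.4.1 and 8.5 |
|---|---|---|
| Event counted | caused by the drug | any adverse event |
| Time at risk | from dosing | from enrolment |
| Patients able to have it | dosed | enrolled, dosed or not |

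**Step 2. Denominator.** Inputs: 18 enrolled in three groups of six (1.4, 8.2.1). Loss before dosing is not stated. Section 8.2.1 cites attrition of up to 45% from other group-therapy trials, but that is total attrition. Placing all of it before dosing is my worst-case assumption: 18 x 0.55 = 9.9, taken as 10 dosed.

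Never-dosed patients contribute no drug-caused events, so:

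all-enrolled rate = (reactions / dosed) x (dosed / enrolled)

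| Dosed of 18 | Factor |
|---|---|
| 18 | 1.00 |
| 17 | 0.94 |
| 16 | 0.89 |
| 15 (one lost per group) | 0.83 |
| 14 | 0.78 |
| 10 (assumed worst case) | 0.56 |

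**Step 3. What this does to a reported rate.** The reaction counts are invented for illustration; intervals are exact (Clopper-Pearson) 95%.

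| Dosed | Reactions | Over dosed | Over all 18 enrolled |
|---|---|---|---|
| 16 | 8 | 50.0% (24.7 to 75.3) | 44.4% (21.5 to 69.2) |
| 15 | 5 | 33.3% (11.8 to 61.6) | 27.8% (9.7 to 53.5) |
| 10 | 5 | 50.0% (18.7 to 81.3) | 27.8% (9.7 to 53.5) |

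**Step 4. Numerator.** Take 16 dosed with 8 reactions, and suppose one of the two undosed patients also has an event. The planned figure is (8 + 1)/18 = 50.0%. That equals 8/16, but only because dilution and an added non-drug event happen to cancel. The formula in Step 2 therefore describes drug-caused events only. It does not predict the direction of error in the any-event percentage.

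**Step 5. By dose.** Section 1.3 gives 0.3 mg/kg to the first group and 0.36 mg/kg to later groups if the first level is well tolerated. With all 18 dosed, that is 6 and 12 patients. For zero events the two-sided 95% upper limit is 1 - 0.025^(1/n): 45.9% for n = 6 and 26.5% for n = 12. Dose also changes with cohort. Counts by dose are therefore descriptive and cannot support a comparison.

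**The case against.** The case for the plan as written is substantial.

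- **The population suits the objective.** Section 2.1.1 concerns the safety of the combined therapy, and the treatment period begins with group session 1. Section 7.1 also bases safety on everyone enrolled. Some patients may taper off medication to take part (footnote to 3.3.2), so pre-dose events are of interest. This stands, and it is why the all-enrolled table should stay.
- **The term in 2.2.1 may be loose.** Its parenthesis points to the DAIDS table, and 8.5 classifies events with that table. If graded adverse events of any cause were meant, 8.5 does summarise them. This partly stands. But the protocol defines adverse reaction separately in 7.3.2 and collects attribution in 7.4, and 8.5 reports no rate by relatedness.
- **The data exist.** Attribution and grade are recorded for each event, adverse events are screened before each of sessions 5-10, and session vital signs and the session rating form exist only for dosed patients. What is missing is a tabulation. That is correct, and it makes the change cheap.
- **The size is hypothetical.** No document gives pre-dose loss. With 16 dosed, the gap between 50.0% and 44.4% is small beside the intervals. This stands.

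Two stronger readings are tempting and not supported. A reader might infer that 5.2 contradicts 8.4.1. It does not: 5.2 calls each dosed subject evaluable but does not say that only dosed subjects are, and dosed patients are a subset of those enrolled. A reader might also infer that Section 8 leaves open whether pre-dose events count. Section 8.5 covers any event in all enrolled, and 7.4 and 7.6 record every event whatever its cause, so the natural reading is that they do count.

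**Conclusion.** The point holds as an omission. The planned safety summary does not deliver a drug-reaction rate, although 2.2.1 read with 7.3.2 makes that rate the basis of primary safety, and 7.4 collects the attribution needed to approach it.

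For drug-caused events, the all-enrolled rate is between 1.00 and 0.56 times the dosed rate with 18 enrolled. The lower end assumes that all of the cited 45% attrition falls before dosing, so it should not be read as an expected understatement of nearly half. If nobody is lost before dosing the denominators agree, and only the pooling of pre-dose and unrelated events remains.

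Neither the choice of all-enrolled nor any stated figure is wrong. The Section 1.4 hypothesis of no treatment-emergent serious events does not depend on the denominator. The conclusion is confined to Section 8: the Data and Safety Monitoring Plan appendix cited in 9.7 was not available for this review, and further tables may be planned there.

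**What to change.** 1. In 8.5, keep the all-enrolled adverse-event table for the combined therapy, and split it by onset before or after dosing.
2. In 8.4.1, add a set of all patients who received psilocybin.
3. In 8.5, report over that set, as the primary drug-safety figure, the percentage of patients with an adverse event starting after dosing and the subset rated possibly, probably or definitely related under 7.4. Give exact 95% intervals for both.
4. State the remaining limit. Attribution in 7.4 covers drug or intervention, and group sessions 5-10 also follow dosing, so the new figure narrows the rate to drug-caused events but does not fully isolate them.
5. Counts by dose received may be listed, marked as descriptive because dose is confounded with cohort.

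The cost is SAP wording and one more descriptive table. The intervals will be wide, and the rates may look less favourable than the all-enrolled ones. The change needs onset timing for each event, by date or at least by visit interval. The documents do not state that an onset date is recorded, so that should be confirmed. No trial procedure changes otherwise.
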